	
Given the small number of patients targeted for study inclusion and anticipated differences in baseline characteristics between afatinib-treated and patients treated with other systemic therapies, statistical comparisons are not planned. In lieu of statistical comparisons between cohorts, the non-afatinib cohort will provide context for interpreting results among those treated with afatinib. Specifically, this context includes what patients with NRG1 gene fusions not treated with afatinib look like, how they are managed and treated, and what their clinical outcomes look like. The non-afatinib cohort will provide a broader understanding of NRG1 gene fusions among patients with solid tumors, for which limited evidence currently exists.
																						
	
Incidence and severity of AEs will be summarized and displayed in number/percentage. All safety endpoints will be analysed descriptively.
																						

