9. RESEARCH METHODS

9.1 STUDY DESIGN

This is a non-interventional, retrospective, US, multi-site, cohort study based on existing data from medical records of patients with *NRG1* gene fusion-positive solid tumors treated with afatinib or other systemic therapy. Two cohorts of patients will be identified. The first includes any patient with *NRG1* gene fusion-positive solid tumors who has received afatinib in any line of therapy (afatinib cohort) between 01/01/2017 and 03/31/2020. The second includes any patient with *NRG1* gene fusion-positive solid tumors who has not received afatinib in any line of therapy (other systemic therapy cohort) during the same period and no history of afatinib use. Follow-up will include at least 3 months after initiation of afatinib or other systemic therapy, unless a patient died prior to 3 months of follow-up.

In total, up to 120 patients with *NRG1* gene fusion-positive solid tumors will be selected for this study, of whom up to 70 will be afatinib-treated and up to 50 will be treated with other systemic therapy. Study objectives are to describe these patients and calculate the ORR in each group, as well as to estimate PFS, TOT, TTP, OS, DOR, and DOCB along with describing the incidence and severity of AEs among patients in the two cohorts. Data to be collect through this medical chart review include patient demographics, clinical characteristics at the time of diagnosis/initiation of a line of therapy, treatment-related data points (dates of initiation, discontinuation, dosing), AEs occurring during therapy, disease response, date of progression and/or death.

Given the small number of patients targeted for study inclusion and anticipated differences in baseline characteristics between afatinib-treated and patients treated with other systemic therapies, statistical comparisons are not planned. In lieu of statistical comparisons between cohorts, the non-afatinib arm will provide context for interpreting results among those treated with afatinib. Specifically, this context includes what patients with *NRG1* gene fusions not treated with afatinib look like, how they are managed and treated, and what their clinical outcomes look like. The non-afatinib arm will provide a broader understanding of *NRG1* gene fusions among patients with solid tumors

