Data collection is anticipated to begin in the third/fourth quarter of 2020, allowing for a minimum follow-up period of 3 months. All patients are required to have initiated index therapy (i.e., afatinib in any line; other systemic therapy among those without any history of afatinib) between 01/01/2017 and 03/31/2020. As such, the maximum follow-up period is approximately 39 months. The index date is the date of initiation of afatinib or other systemic therapy between 01/01/2017 and 03/31/2020 for the other systemic therapy cohort.

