DOR	Duration of response will be calculated as the time from initial response (for any patient with a complete or partial response initially) until the earliest of either disease progression or death. Patients who discontinue therapy due to a reason other than progression will be censored on the date of discontinuation. Patients still on therapy at the time of data cut-off will be censored on their last visit date.
TOT	Time from initiation of a line of therapy until discontinuation for any reason; patients on therapy at the time of data cut-off will be censored on the last date of treatment.
TTP	Time from initiation of a line of therapy until discontinuation due to disease progression; patients on therapy or those who discontinued due to a reason other than disease progression will be censored on the last date of treatment.

PFS	Time from initiation of a line of therapy until disease progression or death; patients on therapy at the time of data cut-off will be censored on the last date of treatment. Patients who discontinue a line of therapy for a reason other than disease progression but who subsequently die prior to the receipt of any other therapy will be considered an event on the date of death.
OS	Time from initiation of any therapy in the metastatic setting until death; patients alive at the time of data cut-off will be censored on the last date the patient was seen by the provider/clinic.
AE	An adverse event is defined as any untoward medical occurrence in a patient administered a medicinal product and which does not necessarily have a causal relationship with this treatment. AEs from a prepopulated list (including “other, please specify”) during each line of therapy will be indicated by providers. The number and proportion of patients experiencing each AE reported during afatinib or other systemic therapy will be reported. See Section 11.1 and Table 3 for further details.

In addition to TOT, to further characterize treatment patterns for those treated with afatinib and those treated with other systemic therapy, the following will be collected (and calculated based on the collected data):

- Treatment history (i.e., regimens, duration, number of cycles, sequence)
- Starting dose of afatinib or other systemic therapy
- Dose modifications of afatinib or other systemic therapy (i.e., dose reductions and their timing, dose increases and their timing, dose delays and their duration and timing)

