- Rationale for afatinib or other systemic therapy discontinuation

AEs will be collected and analyzed in the Clinical Study Report. Providers will be shown information describing what constitutes an AE/ADR/SAE/FAE per BI policies. The processes for safety reporting and analysis of the safety data will be implemented and conducted as per the BI non-interventional study (NIS) standard operating procedures. [REDACTED] will complete any reporting of events to BI per event reporting protocols.

The diagnosis, time, attribution (treatment-related or not per provider interpretation) and severity of the reported AEs during index therapy will be collected. If death is cited as rationale for discontinuation then provider will abstract data related to date of death, cause of death.

Table 3. Adverse events data collection.

Variable	Definition / response options
AEs during a given line of therapy	During each line of therapy, providers will indicate the AE that occurred including severity.
Start date of AE	Date each AE occurred

Severity (see section 11.1)	
Severity of each AE, as assessed by the provider, provided the following guidance:
 
 • Mild (mild symptoms; clinical or diagnostic observations only [e.g. lab work]; intervention not performed) • Moderate (minimal, local or noninvasive intervention performed [e.g., administration of fluids]) • Severe (medically significant ranging from not immediately life-threatening, life-threatening consequences, to death related to AE; [e.g., extensive monitoring, hospitalization or prolongation of hospitalization])
Resolution	
Outcome of each AE will be collected as:
 
 • Recovered/Resolved • Recovered/Resolved with sequelae • Not yet recovered/Not yet resolved • Fatal • Unknown
Outcome	
For all AEs, the outcome of the AE, regardless of severity indicated, will be assessed by participating providers. These outcomes will allow for the classification of serious and fatal AEs as defined in Section 11
 
 • Dose reduction • Dose hold/dose delay/schedule change • Discontinuation of treatment • Unscheduled office visit/treatment • Resulting in death • Life-threatening • Required inpatient hospitalization • Resulted in persistent or significant disability • Prolonged existing hospitalization
End date of AE	Date AE resolved/patient recovered (if resolved/recovered)

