9.7 DATA ANALYSIS

Demographic and clinical characteristics will be reported by descriptive analyses including counts and frequencies for dichotomous and categorical variables, while measures of centrality (mean, median) and spread (min, max, standard deviation, interquartile range, as appropriate) will be used for continuous variables. These characteristics will be described at the time of initial diagnosis of advanced/metastatic disease and at the time of initiation of each line of therapy received, for the afatinib cohort and separately for the other systemic therapy cohort. No statistical comparisons will be made across these two cohorts in terms of demographic, clinical characteristics, and clinical outcomes.

The calculations for all outcomes (e.g., ORR, DOR, DOCB, TOT, TTP, PFS, OS) are defined in **Table 2** in Section **9.3.2 Outcomes**. For disease response, the point estimate for ORR and associated 95% confidence interval (CI) will be calculated for initial response to index therapy (i.e., afatinib or other systemic therapy) and best response to index therapy, for each cohort. ORR will be reported among subgroups within each of the treatment cohorts, by tumor type and line of therapy. The Kaplan-Meier method will be used to estimate time-to-event outcomes (DOR, DOCB, TOT, TTP, PFS, and OS) to account for any right-censoring (e.g., patient had not discontinued therapy, patient had not progressed, or died). Time-to-event outcomes will be described for each of the two treatment cohorts and in subgroups within the two treatment cohorts, according to solid tumor and line of therapy. All study outcomes will be reported separately for those treated with afatinib monotherapy. In the event an outcome cannot be assessed for a given patient, that patient would be omitted from assessment of that outcome; reason for omission in a given outcome assessment will be reported.

Cumulative incidence, severity, and timing of AEs during the index therapy will be summarized and displayed in number/percentage form for each of the treatment cohorts, separately. All safety endpoints will be analyzed descriptively. AE reporting is summarized in Section **11 Management and Reporting of Adverse Events/Adverse Reactions**.

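### AE cumulative incidence is planned only as crude patient percentages, which take no account of time on index therapy or of patients still on therapy at cut-off

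*Combined protocol and SAP*

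**What the plan says.** Objective 5 (Section 8) is to describe how often AEs occur, and how severe they are, during treatment. Three places define the measure:

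- Section 9.7: "Cumulative incidence, severity, and timing of AEs during the index therapy will be summarized and displayed in number/percentage form", separately by cohort, with all safety analysis descriptive.
- Abstract, Data analysis: "Incidence and severity of AEs will be summarized and displayed in number/percentage".
- Section 9.3.2, Table 2: "The number and proportion of patients experiencing each AE reported during afatinib or other systemic therapy will be reported".

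Section 9.7 deals with censoring for other outcomes: "The Kaplan-Meier method will be used to estimate time-to-event outcomes (DOR, DOCB, TOT, TTP, PFS, and OS) to account for any right-censoring". AEs are not on that list.

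Table 2 makes time on treatment (TOT) an outcome in its own right and censors patients who are still on therapy at cut-off. Section 9.1 describes data collection as "allowing for a minimum follow-up period of 3 months", waived for early deaths ("unless a patient died prior to 3 months of follow-up"), with a maximum of about 39 months.

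On data, Table 3 asks for the AE start date ("Date each AE occurred"). Section 9.2 has the form collect dates on which doses were started, stopped and interrupted. Section 9.3.2 adds "Treatment history (i.e., regimens, duration, number of cycles, sequence".

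**The concern.** AEs are counted only while the patient is on index therapy, so a patient treated for longer has more time in which to have one. A crude percentage mixes the rate at which AEs arise with the length of treatment. Between two groups with the same steady rate, the one that stops sooner shows the lower percentage.

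Censoring is a second, separate problem. A patient still on therapy at cut-off may have a first AE later, but stays in the denominator as event-free. Section 9.7 uses the term cumulative incidence without saying how it is estimated or to what time point, so the reported figure has no defined horizon.

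This matters for Objective 5 in each cohort on its own. It also matters because Section 9.1 offers the non-afatinib cohort as context for reading the afatinib results, and the Abstract lists AEs among the clinical outcomes.

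**Working it through.** **Figures in the plan.** The documents state no AE rate, expected TOT or proportion still on therapy, so there is no planned AE figure to reproduce. The one related figure is the maximum follow-up. From 01/01/2017 to 03/31/2020 is 1,185 days, and 1,185 / 30.4375 = 38.9 months. The stated 39 months is thus the length of the index window. Counted to 1 July or 31 December 2020, the earliest patients could have about 42 or 48 months. These are spans of follow-up, not of treatment.

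**Steady AEs.** Assume a constant first-AE rate r per month and exponential TOT with mean e months, with every patient followed to the end of treatment. The proportion with an AE on treatment is r / (r + 1/e).

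| Assumed r | e = 3 | e = 6 | e = 9 | e = 12 |
|---|---|---|---|---|
| 0.05 | 13% | 23% | 31% | 38% |
| 0.10 | 23% | 38% | 47% | 55% |

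For example, 0.05 / (0.05 + 0.3333) = 0.130 and 0.05 / (0.05 + 0.0833) = 0.375.

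**Early-onset AEs.** Assume instead that 60% of patients are prone to the AE, with exponential onset of mean k months. With median TOT m, the proportion is 0.6 × (1/k) / (1/k + ln 2/m). The steady case is put on the same median scale as r / (r + ln 2/m).

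| Assumed pattern | m = 3 | m = 12 | Difference |
|---|---|---|---|
| Steady, r = 0.02 | 8.0% | 25.7% | 17.7 points |
| Steady, r = 0.05 | 17.8% | 46.4% | 28.6 points |
| Steady, r = 0.10 | 30.2% | 63.4% | 33.2 points |
| Early, k = 0.5 | 53.8% | 58.3% | 4.5 points |
| Early, k = 1 | 48.7% | 56.7% | 8.0 points |

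The dependence on exposure is therefore set mainly by the onset pattern, which the documents do not give.

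**What a fixed-time incidence achieves.** With discontinuation as a competing event at rate d = 1/e, the 3-month cumulative incidence is r / (r + d) × (1 − exp(−3(r + d))). At r = 0.05:

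- e = 3: 0.1304 × (1 − exp(−1.15)) = 8.9%
- e = 12: 0.375 × (1 − exp(−0.40)) = 12.4%

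The gap narrows but does not close. This measure fixes the horizon and handles censoring; it remains an on-treatment risk that depends on how long treatment lasts. Only the person-time rate removes that dependence, and only if the rate is constant.

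**Censoring.** None of these illustrations contains patients still on therapy at cut-off. That part of the gap follows from the planned method, but it cannot be sized.

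**The case against.** Patient percentages are a legitimate way to describe AE incidence. The plan rules out statistical comparisons between cohorts (Section 9.7), says crude ones cannot be made (Section 9.9), and in the ENCePP checklist says the second cohort is not a comparator. AE timing is to be summarised, and TOT is estimated by Kaplan-Meier in each cohort, so readers will see exposure reported as well. In the uncensored illustration, the crude percentage equals the eventual on-treatment cumulative incidence. It is then a different quantity from a rate, not a biased estimate. The inputs may also be weak: Section 9.4 allows non-required items to be missing, Section 10 names event dates only for serious or fatal AEs and progression, and Section 9.9 admits under-documentation of AEs.

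Most of this stands, and it limits the point to an improvement. It does not close the gap. Separate summaries of TOT and AE timing do not let a reader derive a first-event rate. Descriptive status does not tell the reader what horizon a percentage refers to, or how patients still on therapy were handled. The caution in Section 9.9 about AE frequency concerns under-reporting, not unequal exposure.

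A reader might infer that time on index therapy is known to vary widely, or that the percentages reflect exposure as much as AE risk. The documents support neither: they give a range of follow-up, no TOT distribution and no AE onset pattern.

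**Conclusion.** The point holds as a gap in the specification. The AE percentages are unadjusted for time on index therapy, and patients still on therapy without an AE so far are counted as AE-free. The effect ranges from about 5 to 8 points for the early-onset AEs illustrated to about 29 points for a steady AE at 0.05 per month, each for median TOT of 3 against 12 months. All rates, onset patterns and durations are assumptions, and exponential TOT is assumed throughout.

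It would go too far to call the planned percentages wrong or a person-time rate the one correct measure. The rate rests on a constant hazard, and for early-onset AEs longer treatment dilutes it. Nor does the point show a biased cohort comparison, since none is planned. It is a low-cost improvement that does not threaten the study's conclusions.

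**What to change.** Keep the number/percentage tables. In Section 9.7, define what cumulative incidence of AEs means, and add for each cohort:

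- First-event AE rates per 100 patient-months on index therapy, with 95% CI: patients with the event, divided by time from start of index therapy to the first event, end of therapy or cut-off. State the constant-rate assumption.
- Cumulative incidence of first AE at a stated time, such as 3 months, by the Aalen-Johansen estimator. Censor patients still on therapy at cut-off and treat discontinuation and death as competing events. Describe it as on-treatment risk that still depends on treatment duration. Because eligibility requires 3 months of follow-up unless the patient died, censoring before 3 months should be slight; it would matter more at a later time point.

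Report the number of AEs with missing onset dates, and draw no formal cohort comparison. Table 3 and Section 9.2 already provide for the dates, so no new data item is needed. The cost is one or two more tables, and rates that will be imprecise where onset dates are missing.

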9.8 QUALITY CONTROL

[REDACTED] will conduct all data quality assurance and control activities. The following sections outline the data quality assurance and control measures implemented throughout data collection, management, and inspection, prior to constructing a final analytic data file. These procedures are conducted from a programming standpoint (e.g., logic checks built into the data collection tool) via statistical analysis to identify patterns and outliers, and by clinical review to identify implausible data or incongruent data points on a given patient.

9.8.1 eCRF Functionality Testing

Prior to data collection and during the field test, [REDACTED] will test the eCRF. This quality control process begins with extensive testing of the eCRF to ensure functionality across web-based user environments, looping logic to ensure proper alignment of data-related fields (required responses to certain fields prior to entering data into subsequent field), and other programmatic checks to ensure the reduction of the input of erroneous data (such as specifying maximums for year of birth or initiation of treatment within the dates of the enrollment period). Only data ranges consistent with known clinical parameters will be allowed to be entered into the eCRF.

In addition, the eCRF will be field-tested among four providers to ensure its functionality, the correct interpretation of the questions in relation to the data points of interest, and the length of time required for completion for a single patient. Field-testing includes a [REDACTED] researcher viewing the screen of the provider completing the eCRF with actual patient data and asking probing questions regarding the functionality, interpretability (variables are aligned with clinical definitions or clinical interpretations), and availability of the variables requested. No data from the pre-testing phase will be used in the analysis for this research. Pre-testing of the eCRF will not commence until receiving IRB approval for the conduct of the study. The pre-test results will be reviewed by BI with [REDACTED] however, BI will not have access to the individual data collected. Any changes made to the eCRF document as a result of the pre-test will require the resubmission of the eCRF and study protocol to the IRB.

9.8.2 Data Validation

Multiple levels of quality control and quality assessment occur during the study. First, the eCRF includes programmed internal validity checks, including date validation (e.g., date of initiation of index therapy cannot occur before date of initial diagnosis of cancer) and logic that forces providers to respond to required questions. Next, the eCRF will be pre-tested with four clinicians prior to data collection. During this pre-test, [REDACTED] staff will hold a web-based conference with a selected provider during which the provider will abstract data into the eCRF while [REDACTED] research staff members monitor and probe the provider regarding the clarity of eCRF data fields. After conducting this pre-test, [REDACTED] will present findings to BI and suggest revisions to the eCRF as needed. The revised eCRF will be filed with the study IRB.

During data collection, [REDACTED] clinical research staff review all submitted eCRFs inspecting each for implausible patient clinical profiles based on treatment sequencing, lab and radiology results, or outcomes that are inconsistent with known clinical parameters, or other clinical data that are inconsistent with known standards and outcomes. In addition to review of the submitted data by the clinical research team, the study statistician will conduct an analysis of submitted data to identify any data points inconsistent (outliers) with the study population average. This analysis will include a descriptive analysis of the provider characteristics, demographics, baseline clinical and disease characteristics, and characteristics of treatment patterns (e.g., TOT). Data points flagged as outliers will be delivered to the clinical research team for further assessment.

Should outliers be discovered, [REDACTED] clinical research would contact the provider submitting the eCRF for data validation. All providers are informed in their contractual agreement that

follow-up with clinical staff at [REDACTED] may be required. Participating providers are asked to create a 4-digit unique identifier code per patient that is provided to [REDACTED] through the eCRF and used for identifying the patient record for validation between [REDACTED] and the provider. Individual eCRFs will be removed from providers unable to validate a data point, and resampling will not occur. All other data will be considered valid provided additional patients from that provider are not selected for random validation.

Random data validation occurs by selecting a random eCRF from each provider submitting a patient. Providers who have been previously verified by [REDACTED] will not be subject to completion of the random validation. A verified provider is any physician abstractor who has completed at least two of the following: (1) completed and acknowledged our web-based chart data abstraction training in the past 2 years, (2) participated in a chart review pre-test with screen sharing, (3) participated in 2 previous chart review studies in the past 2 years and accurately validated data, and (4) have completed a phone interview with the [REDACTED] team for data validation. A provider may be verified but still required to answer questions regarding patients with data flagged by [REDACTED] or [REDACTED] groups. Providers subject to random validation are asked to complete a 3-data point validation exercise for the patient whereby the provider is given the unique patient identifier but no other information. The provider is asked to re-enter the respective data elements. The three data points may include elements such as the month/year of index treatment initiation, stage at diagnosis, and date of index treatment discontinuation (or date of last treatment/prescription if patient is still on therapy). A provider who fails to validate all data points for a selected patient will be required to submit to further clinical data review. Patients for whom the data are deemed questionable by the research team staff will be excluded; providers will not be compensated for excluded data. No resampling to replace the excluded eCRF will occur. Provider who are nonresponsive to any validation request will have all data submitted excluded from the study.

For all data validation processes, a log of records that undergo statistical and clinical review will be kept, recording the reason a given record was flagged for further follow-up. Should data quality checks and confirmation with providers reveal discrepancies, corrections will be made to the database. These corrections (including whether a record was dropped entirely) will be documented in an audit trail. The number of records undergoing each step of data validation and the number of records corrected or excluded from the final data set will be reported.

